As previously described, VR interventions have been used as distractions or diversions during medical procedures. This study will be one of the first RCTs to test deployment of low-cost VR as an adjunct to opioid pain management in an inpatient hospital setting. The VR hardware configuration and all software is currently being developed by AppliedVR, a leader in the development of medical applications for virtual reality technology, including interventions for weight loss and health, safety training, education, and personal development. Details about the VR hardware use can be found at the end of this document (See **VR Manual** in **Additional Information**), and are summarized below.

VR Hardware:

This RCT will utilize a Samsung Gear VR goggle set, fitted with a Samsung Galaxy phone that delivers VR images and sound (Figure 1a). Users will wear the VR goggles as shown in Figure 1b. Study staff will familiarize inpatients with hardware before use, and allow them to test use on their own before leaving the initial visit.

Figure 1. VR Hardware

1a. VR Goggles and Phone

1b. VR Goggles on user

VR Hardware Placement and Cleaning:

The Samsung gear device will be put in place as follows:

1. Patient places sanitary hairnet on head
2. Goggle is fitted with disposable foam backing affixed to inside of face mask
3. Study coordinator places goggle headset on patient and adjusts straps

Between patients, the device will be cleaned as follows:

1. Disposable hairnet on patient and foam backing will be thrown in sanitary waste bin in inpatient room.
2. Fabric strap will be cleaned by coordinator using Virex, approved cleaner for medical fabrics and let sit for a minimum of 10 minutes before next use.
3. Plastic housing of device will be cleaned using Sani-wipes and let sit for a minimum of 2 minutes before next use.
4. Inside and outside of the lenses of device will be cleaned using approved lens cleaner containing alcohol.

VR Software:

In VR, 3D visual and audio cues immerse the patient. Software modules may be used as needed during the inpatient stay for as long as a patient wishes. We are requiring 10 minutes for initial test use in the presence of study staff, and then recommending a maximum of 30 minutes at a time, each followed by 15 minute breaks. Patients will be shown how to select VR experiences from the phone menu (Figure 2).

Figure 2. VR Software Menu

VR interventions include the following (see Figure 3):

Figure 3. VR Environment Examples

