For patients randomized to the experimental condition, the study staff member will arrive at bedside, explain the risk and benefits of the study, and will obtain informed consent. Patients will be advised that standing puts them at risk for a fall, and that they should remain seated for each VR intervention. Next, the study staff member will explain the use of the Samsung VR goggle set, and thereafter will allow the patient to use the device freely for up to 30 minutes at a time. An interval of 10 minutes is suggested for first-time use, but patients will be allowed to continue as long as they are not experiencing any

discomfort or side effects (dizziness, motion sickness, etc.). The study staff member will be present during the initial visit, and will work with hospital staff as necessary to ensure the patient is receiving appropriate clinical care throughout the duration of the intervention.

Salivary cortisol will be collected as an optional procedure twice, pre and post demonstration of VR and the Health and Wellness channel.

Collection Instructions:

1. Do not brush teeth before collecting specimen.
2. Do not eat or drink for 15 minutes prior to specimen collection.
3. Do not use any creams, lotions or steroid inhalers immediately prior to the collection.
4. Collect specimen and record collection time.
5. To use the Salivette:
 - a. Rinse mouth thoroughly with water and discard.
 - b. Remove top cap of container to expose swab.
 - c. Place swab directly under the tongue until well saturated, approximately 1 minute.
 - d. Do not touch swab with fingers.
 - e. Place swab back into its container without touching, and replace the cap.
6. Record collection time, and send appropriately labeled Salivette to laboratory.

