Patients using the virtual reality intervention may experience side effects common to users of VR and individuals who view 3D video, including motion sickness, dizziness, eye strain, headaches, or other visual abnormalities. If patients experience these symptoms, they will be asked to stop using the VR software for 15 minutes, and will be allowed to continue *if* they agree and wish to proceed. A small number of patients (up to 0.025%) may experience seizures or severe symptoms (e.g., disorientation, nausea, or drowsiness) upon viewing the virtual reality experience. Seizures from flashing light are more common in children and epileptic patients (who are excluded). To minimize this concern further, we have *not* incorporated flashing lights into the VR experiences. Some patients may find the VR goggles uncomfortable to wear or confining. To date, patients with claustrophobia have *not* reported discomfort using VR goggles, as they are often used in treatment of that condition. Nevertheless, individuals previously diagnosed with claustrophobia should discontinue use if they feel uncomfortable. A trained study staff member will be on hand during initial use to ensure patient safety. Patients who use the VR headset over several days are instructed to use it for a maximum of 30 minutes at a time. In pilot testing, patients have not reported any adverse effects from extended use of VR hardware.

Subjects may feel uncomfortable or embarrassed when answering survey questions. If subjects are uncomfortable or embarrassed answering any survey question, they may skip it. The survey will be labeled with a unique study number so that only the research team can recognize subjects.

Data Security and Privacy:

Data will be abstracted from the EHR by approved staff ([name] and other authorized personnel), and will be transmitted securely to study staff. Staff data collection will be limited to variables mentioned previously. Demographic and clinical data, as well as Qualitative Interview responses will be entered into a secure database and stored on secure servers at CSMC. We will not collect Social Security numbers,

and we will use sequential Unique ID numbers to track patients in the study. All collected specimens will be de-identified before they are sent out to Quest Diagnostics for analysis.

Conclusion:

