Some people (about 1 in 4,000) may have severe dizziness, seizures, epileptic seizures or blackouts triggered by light flashes or patterns, and this may occur while they are watching TV, playing video games or experiencing virtual reality, even if they have never had a seizure or blackout before or have no history of seizures or epilepsy. Such seizures are more common in children and young people under the age of 20. Anyone who has had a seizure, loss of awareness, or other symptom linked to an epileptic condition should consult with a doctor before using the Samsung Gear™ VR Innovator's Edition.

General Instructions and Precautions

- Use only in a safe environment. The Gear VR produces an immersive virtual reality experience that distracts you from and blocks your view of your actual surroundings. Always be aware of your surroundings when using the Gear VR and remain seated at all times. Take special care to ensure that you are not near other people, objects, stairs, balconies, windows, furniture, or other items that you can bump into or knock down when using — or immediately after using— the headset. Do not handle sharp or otherwise dangerous objects while using the Gear VR Innovator's Edition. Never wear the Gear VR in situations that require attention, such as walking, bicycling, or driving.
- Make sure the Gear VR headset is level and secured comfortably on your head, and that you see a single, clear image.
- Ease into using the Gear VR to allow your body to adjust. Use it for only a few minutes at a time at first, and increase the amount of time using the Gear VR gradually as you grow accustomed to virtual reality. Looking around when first entering virtual reality can help you adjust to any small differences between your real world movements and the resulting virtual reality experience.
- A comfortable virtual reality experience requires an unimpaired sense of motion and balance. Do not use the Gear VR when you are tired, need sleep, are under the influence of alcohol or drugs, are hung-over, have digestive problems, are under emotional stress or anxiety, or when

suffering from cold, flu, headaches, migraines, or earaches, as this can increase your susceptibility to adverse symptoms.

- Take at least a 10 to 15 minute break every 30 minutes, even if you don't think you need it. Each person is different, so take more frequent and longer breaks if you feel discomfort. You should decide what works best.

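### The Risks section lets a patient with VR side effects restart after 15 minutes on agreement alone, contradicting the restart rule in the appended VR manual

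*Combined protocol and SAP*

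**What the plan says.** The Risks part of Risks and Benefits names five side effects common to VR users: motion sickness, dizziness, eye strain, headaches and other visual abnormalities. For a patient who has any of them, the rule is that "they will be asked to stop using the VR software for 15 minutes, and will be allowed to continue" on condition that "they agree and wish to proceed". The same paragraph states: "A trained study staff member will be on hand during initial use to ensure patient safety".

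Other parts of the document touch on the same situation:

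- **Experimental Group, Pre-Intervention Procedures (first session).** The first use is suggested to last 10 minutes, and "patients will be allowed to continue as long as they are not experiencing any" "discomfort or side effects (dizziness, motion sickness, etc". The headset is left in the room only if the patient reports no adverse effects after that supervised run.
- **VR Manual, Frequently Asked Questions.** A patient who feels unwell sits for 15 minutes. Staff make sure that the patient feels better before leaving and look in again the same day.
- **VR Manual, Discomfort.** The user stops immediately on any listed symptom and does not use the device again until every symptom has been fully gone for several hours.

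The protocol's description of the VR intervention refers the reader to this manual for details of hardware use.

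**The concern.** As written, the Risks rule has two conditions: 15 minutes have passed, and the patient is willing. A patient who is still dizzy at 15 minutes and wants to go on meets both. The manual at the end of the same document forbids exactly this.

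The stake is the safety of inpatients using the headset on their own. After the first session the headset can remain in the room for up to 20 days, and most use is expected when the patient is not receiving clinical care. In that period no trained person is stated to be present to judge whether symptoms have settled, so the written restart rule has to do that work. The protocol already recognises a fall risk, since patients are told to stay seated. The current phase enrols hospitalised orthopedic patients, and VR is given as an adjunct to opioids.

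**Working it through.** No stated figure needs reproducing and no power or error-rate calculation applies. The check is a comparison of the texts.

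**1. Does the Risks rule contain a symptom condition?** No. The sentence gives a pause and the patient's agreement. No other part of the document adds a resolution condition to it by reference.

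**2. Do the two restart rules cover the same symptoms?**

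| Symptom in Risks | Counterpart in VR Manual, Discomfort |
|---|---|
| Motion sickness | symptoms similar to motion sickness |
| Dizziness | dizziness |
| Eye strain | eye strain |
| Headaches | pain or discomfort in the head or eyes |
| Other visual abnormalities | altered, blurred or double vision, other visual abnormalities |

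All 5 of 5 are covered, so the two rules address the same event.

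**3. What does each text require?**

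| Text | Situation governed | Symptom condition | Time |
|---|---|---|---|
| Risks | restart after symptoms | none | 15 min |
| Manual, Discomfort | restart after symptoms | all symptoms completely gone | several hours after they have gone |
| Manual, FAQ | looking after an unwell patient | feels better, before leaving | 15 min, plus a same-day check |
| Pre-Intervention Procedures | carrying on during the first session | no discomfort or side effects | not stated |

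Only the first two rows are explicit restart rules, and they conflict. The other two show the intent that symptoms should settle, but neither says when VR may begin again after a pause.

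**4. Is the gap closed elsewhere?** Each safeguard lowers the risk, but none sets a condition for restarting:

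- Exclusion Criteria remove patients sensitive to motion and those with a condition making them prone to frequent nausea or dizziness. The Risks section still expects these side effects in those enrolled.
- The symptom-free test run screens the first exposure only.
- The daily status check is made through the patient's provider.

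**5. How many patients?** The planned VR arm is 122. For the orthopedic cohort it is 160 / 2 = 80, less orthopedic VR patients enrolled before October 2017, whose number is not given. These are ceilings on exposure, not counts of harm. The only rate in the protocol's own Risks text, up to 0.025%, is for seizures or severe symptoms, not for the five common ones. The pilot statement of no adverse effects from extended use has no denominator. The number affected therefore cannot be computed.

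**The case against.** The strongest reply is that the document already protects these patients. If the manual applies, a resolution requirement exists and only the wording of a Risks paragraph is out of step. If it does not apply, it is general consumer-device advice and a weak standard. Patients who react badly at first exposure never keep the headset, motion-sensitive patients are excluded, users are consenting adults told to stay seated, and a patient's own wish to go on is an informal check on symptoms that only the patient can feel.

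Much of this stands as to the size of the risk, but it does not remove the defect. If the manual applies, staff hold two contradictory instructions; if it does not, no restart condition on symptoms exists at all. Either way the Risks sentence needs the missing clause.

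A reader might also infer more than the documents support:

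- **That three other texts all contain a resolution requirement for restarting.** They do not. The first-session rule governs carrying on under supervision, and the FAQ asks for improvement, not resolution, as a condition of leaving.
- **That the trial must adopt the manual's wait of several hours.** The documents do not say that the manufacturer's section binds in full. Its precautions also advise against use by people who "are under the influence of alcohol or drugs, are hung-over, have digestive problems, are under emotional stress or anxiety", which sits awkwardly with inpatients receiving opioids or under the care of gastroenterology. No evidence is given for either interval.
- **That the pause is inadequate because it equals the routine break.** The protocol is "recommending a maximum of 30 minutes at a time, each followed by 15 minute breaks" for everyone, and the manual's advice is "Take at least a 10 to 15 minute break every 30 minutes". A stop prompted by symptoms and a recommended rest between sessions are different things, and their similar length is no evidence of harm.

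The consent pages are not in the published text, so nothing is claimed about what patients are told there.

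**Conclusion.** The concern holds in this form: the Risks section allows VR to restart after 15 minutes on agreement alone, and this directly contradicts the restart rule in the VR manual that forms part of the same document. It is a looser stated rule, not just a missing detail, and it matters mainly for later use without staff present.

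The conclusion rests on the wording of the two rules and on the statement that trained staff are on hand at initial use. It needs no assumption about how often symptoms occur. The size in patients is unknown, with the 122 planned VR patients as the ceiling. Sample size, power, error rates and the planned comparisons are untouched. It is best classed as a cheap improvement for patient safety.

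**What to change.** Replace the restart sentence in Risks with wording such as:

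> Patients with these symptoms will stop using VR at once, for at least 15 minutes, and may resume only if all symptoms have completely resolved and they agree to go on.

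Put the same restart condition in the manual's FAQ on the patient who does not feel well.

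This removes the conflict over whether symptoms must have gone. It leaves open how long to wait after they have gone, where the manual says several hours. That is a trade-off between caution and VR exposure for the investigators to settle, and the fix does not depend on it.

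The cost is two small wording changes and slightly less VR exposure in patients still symptomatic at 15 minutes. Patients whose symptoms clear within 15 minutes lose no time compared with the current rule. Eligibility, sample size and the analysis plan stay as they are.

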Please note: Questions 1-25 in this survey are part of a national initiative to measure the quality of care in hospitals. OMB #0938-0981

Please answer the questions in this survey about your stay at the hospital named on the cover letter. Do not include any other hospital stays in your answers.

YOUR CARE FROM NURSES

1. During this hospital stay, how often did nurses treat you with courtesy and respect?
 - ¹ Never
 - ² Sometimes
 - ³ Usually
 - ⁴ Always
2. During this hospital stay, how often did nurses listen carefully to you?
 - ¹ Never
 - ² Sometimes
 - ³ Usually
 - ⁴ Always

3. During this hospital stay, how often did nurses explain things in a way you could understand?
 - ¹ Never
 - ² Sometimes
 - ³ Usually
 - ⁴ Always
4. During this hospital stay, after you pressed the call button, how often did you get help as soon as you wanted it?
 - ¹ Never
 - ² Sometimes
 - ³ Usually
 - ⁴ Always
 - ⁹ I never pressed the call button

YOUR CARE FROM DOCTORS

1. **During this hospital stay, how often did doctors treat you with courtesy and respect?**
¹ Never
² Sometimes ³ Usually ⁴ Always
2. **During this hospital stay, how often did doctors listen carefully to you?**
¹ Never
² Sometimes ³ Usually ⁴ Always
3. **During this hospital stay, how often did doctors explain things in a way you could understand?**
¹ Never
² Sometimes ³ Usually ⁴ Always

THE HOSPITAL ENVIRONMENT

4. **During this hospital stay, how often were your room and bathroom kept clean?**
¹ Never
² Sometimes ³ Usually ⁴ Always
5. **During this hospital stay, how often was the area around your room quiet at night?**
¹ Never
² Sometimes ³ Usually ⁴ Always

CARE Channel Infographic

VR Manual

Samsung Gear VR Instructions

Launching a VR Application

1. Power up phone with the button on the right side of the phone. Hold down until the phone vibrates and turns on.

2. To launch a virtual reality application, select one of icons from the grey dock in the lower screen.
3. Follow the prompt: "To open this application, insert your device into your Gear VR."

Attach a Mobile Device

1. With the screen facing toward the headset, attach the device to the Gear VR using the **Power/Accessory Interface Connector** (1).
Note: Make sure the back cover of your mobile device is securely fastened before attaching it to your headset.
2. Press the device into position until the **Phone lock** clicks (2).
3. Attach the window cover to the front of the headset over the mobile device.

Wearing the Gear

1. Align your face and the foam cushioning and put on the Gear VR. **Caution! Do not walk or drive while wearing the Gear VR. Always be aware of your surroundings while using the Gear VR to avoid injury to yourself or others.**

Frequently Asked Questions

How long should a patient wear this?

The experiences run between three and thirty minutes in duration. However, VR experiences are safe as long as the patient is comfortable.

What should be done if a patient does not feel well (dizzy, sick, etc.)?

Please ask the patient to close his or her eyes, which will break the experience, then safely remove the goggles from the patient's head. Have them sit down for 15 minutes. Make sure they feel better before they leave and check up on them later on that day.

Can I wear my glasses inside of the Samsung Gear VR headset?

No, glasses should not be worn as the product was not designed to accommodate them and your glasses could scratch the non-replaceable lenses inside of the headset. The focus dial located on the top of the headset can be used to adjust the image for nearsighted individuals.

The Gear VR doesn't fit well when I put it on, especially around my nose area. Am I doing something wrong?

There are a number of straps on the headset that can be adjusted for comfort. If you are experiencing discomfort in the nose area, tightening the strap that goes over the top of your head will remove the pressure from the bridge of your nose and move the side straps up from your ears. Tightening too much, however, will shift the weight of the headset on your head. The side straps will adjust the tightness of

the headset and foam on your face. Try not to over-tighten as this will lead to discomfort during longer sessions.

Can I stand up and walk around while using the Samsung Gear VR Innovator Edition?

The Gear VR is designed for seated experiences.

When I plug in the phone after the prompt “to open this application, insert your device into your Gear VR,” the application does not load or it loads the wrong screen. Am I doing something wrong?

Please unplug the phone from the Gear VR, return to the home screen with the bottom center button, and restart the process by selecting the application icon and plugging in the phone.

I do not see the application load once I plug in the phone.

Please make sure the Gear VR is completely connected to the phone’s Micro USB port.

Samsung’s Gear VR Health and Safety Information

Some people (about 1 in 4,000) may have severe dizziness, seizures, epileptic seizures or blackouts triggered by light flashes or patterns, and this may occur while they are watching TV, playing video games or experiencing virtual reality, even if they have never had a seizure or blackout before or have no history of seizures or epilepsy. Such seizures are more common in children and young people under the age of 20. Anyone who has had a seizure, loss of awareness, or other symptom linked to an epileptic condition should consult with a doctor before using the Samsung Gear™ VR Innovator's Edition.

General Instructions and Precautions

- Use only in a safe environment. The Gear VR produces an immersive virtual reality experience that distracts you from and blocks your view of your actual surroundings. Always be aware of your surroundings when using the Gear VR and remain seated at all times. Take special care to ensure that you are not near other people, objects, stairs, balconies, windows, furniture, or other items that you can bump into or knock down when using — or immediately after using— the headset. Do not handle sharp or otherwise dangerous objects while using the Gear VR Innovator's Edition. Never wear the Gear VR in situations that require attention, such as walking, bicycling, or driving.
- Make sure the Gear VR headset is level and secured comfortably on your head, and that you see a single, clear image.
- Ease into using the Gear VR to allow your body to adjust. Use it for only a few minutes at a time at first, and increase the amount of time using the Gear VR gradually as you grow accustomed to virtual reality. Looking around when first entering virtual reality can help you adjust to any small differences between your real world movements and the resulting virtual reality experience.
- A comfortable virtual reality experience requires an unimpaired sense of motion and balance. Do not use the Gear VR when you are tired, need sleep, are under the influence of alcohol or drugs, are hung-over, have digestive problems, are under emotional stress or anxiety, or when

suffering from cold, flu, headaches, migraines, or earaches, as this can increase your susceptibility to adverse symptoms.

- Take at least a 10 to 15 minute break every 30 minutes, even if you don't think you need it. Each person is different, so take more frequent and longer breaks if you feel discomfort. You should decide what works best.
- Listening to sound at high volumes can cause irreparable damage to your hearing. Background noise, as well as continued exposure to high volume levels, can make sounds seem quieter than they actually are. Due to the immersive nature of virtual reality, do not use the Gear VR with the sound at a high volume, so that you can maintain awareness of your surroundings and reduce the risk of hearing damage.

Discomfort

- Immediately discontinue use if you experience any of the following symptoms while using the Gear VR Innovator's Edition: seizures; loss of awareness; eye strain; eye or muscle twitching; involuntary movements; altered, blurred, or double vision or other visual abnormalities; dizziness; disorientation; impaired balance; impaired hand-eye coordination; excessive sweating; increased salivation; nausea; lightheadedness; discomfort or pain in the head or eyes; drowsiness; fatigue; or any symptoms similar to motion sickness.
- Do not drive, operate machinery, or engage in other visually or physically demanding activities that have potentially serious consequences (i.e., activities in which experiencing any symptoms could lead to death, personal injury, or damage to property), or other activities that require unimpaired balance and hand-eye coordination (such as playing sports, riding a bicycle, etc.) until you have fully recovered from any symptoms.
- Do not use the Gear VR until all symptoms have completely subsided for several hours. Make sure you have properly configured the Gear VR before resuming use.
- Be mindful of the type of content that you were using prior to the onset of any symptoms, because you may be more prone to symptoms based upon the content being used.
- Consult with a doctor if you have serious and/or persistent symptoms.
